1. OBJECTIVES

1.1 Study Design

We will conduct a randomized placebo-controlled trial in patients with higher-risk monoclonal gammopathy of undetermined significance (MGUS) and low-risk smoldering multiple myeloma (SMM) to test the efficacy of metformin in reducing clinical indicators of disease progression in MGUS and SMM patients. The target enrollment of the trial is 60 patients. After informed consent is signed, participants will be randomized in equal numbers to metformin or its corresponding placebo. The treatment period for the trial is 6-months, with study assessments for the trial's primary outcome occurring at baseline and at the end of the 6-month treatment period. Participants will have the option to learn their treatment assignment after primary (6-month) outcome assessments are complete, and individuals randomized to metformin will have the opportunity to continue to take metformin for an additional 6-months to allow for the observation of potentially longer-term treatment response. Participants who choose to be unblinded and are taking placebo will discontinue study medication. Passive follow-up via medical record review will occur for up to 5 years post-randomization.

1.2 Primary Objectives

To determine whether metformin can reduce or stabilize serum monoclonal (M-)protein concentrations from baseline to 6-months in patients with MGUS and SMM.

1.3 Secondary Objectives

- Identify changes in m-protein/light chains using mass spectrometry.
- Identify changes in hemoglobin concentrations among patients treated with metformin vs. placebo.
- To examine molecular evolution of the tumor cells in response to metformin.
- To determine the impact of metformin on the immune landscape of individuals with MGUS/SMM.
- To explore the degree to which metformin changes plasma metabolites and metabolomic signatures.
- To examine the impact of the metformin on changes in quality-of-life indicators from baseline to 6-months.
- To understand patients' willingness to continue to take metformin beyond the 6-month primary assessment period.
- To examine the response trajectory in individuals who choose to take metformin for up to 1-year.

2. BACKGROUND

2.1 Myeloma (MM) and its Precursor Conditions.

Multiple Myeloma (MM) is an incurable and fatal malignancy, with a 5-year survival rate of just over 50%.¹ The incidence rate of MM in the US has been steadily rising; few cancers have

demonstrated a greater increase in incidence since 2004.¹ MM is a plasma cell dyscrasia characterized by the proliferation of clonal plasma cells in the bone marrow and the production of monoclonal immunoglobulin and/or light chain, with subsequent end organ damage.²

MM always evolves from precursor states of monoclonal gammopathy of undetermined significance (MGUS) and smoldering MM (SMM), which are relatively common blood conditions affecting ~3% of the general population over 50 years.² Both conditions are often clinically detected through the presence of abnormal proteins called “monoclonal (M-)proteins” in the blood and/or urine. In 2010 the International Myeloma Working Group (IMWG) defined monoclonal gammopathy of undetermined significance (MGUS) by the presence of serum M-protein < 3g/dL, clonal plasma cell population in the bone marrow < 10%, and the absence of end-organ damage such as hypercalcemia (serum calcium \geq 11.5 mg/dL), renal insufficiency (serum creatinine \geq 2 mg/dL), anemia (hemoglobin value below the lower limit of normal by more than 2 g/dL or hemoglobin value < 10 g/dL) and lytic bone lesions (CRAB features) that can be attributed to the plasma cell proliferative disorder.³ Smoldering multiple myeloma was defined by the presence of serum M-protein \geq 3 g/dL or IgA $>$ 2g/ dL or urinary monoclonal protein $>$ 500 mg/ dL and/or clonal bone marrow plasma cells \geq 10% and the absence of CRAB features clinically.

In general, MGUS progresses to overt MM at a slow rate of 1% per year, but in some patients, the risk may be as high as 58% in 20 years.^{4,5} SMM has an annual risk of progression of 10%, but in some patients, risk is considerably higher.⁴ These conditions also confer a decreased life expectancy compared to the general population^{6,7}, raising the possibility that there are other disorders associated with MGUS and SMM that have yet to be determined.

2.2 Clinical Management of MGUS and SMM and Status of Treatment.

The cornerstone of management for both entities is to delay therapy until progression to MM, at which time patients have overt end-organ damage.^{8,9} It is therefore unsurprising that patients with MGUS and SMM report high levels of anxiety and distress about their conditions,¹⁰ and cure is seldom achieved.¹¹ However, this paradigm may change as there are already clinical trials that show that early use of MM therapies in the precursor setting may alter the natural history of the disease¹², and importantly, may improve survival.¹³ For example, in a randomized open-label phase 3 trial¹³, 119 patients with high-risk smoldering myeloma were randomized to treatment or observation. Patients in the treatment group received an induction regimen (lenalidomide at a dose of 25 mg per day on days 1 to 21, plus dexamethasone at a dose of 20 mg per day on days 1 to 4 and days 12 to 15, at 4-week intervals for nine cycles), followed by a maintenance regimen (lenalidomide at a dose of 10 mg per day on days 1 to 21 of each 28-day cycle for 2 years). The primary endpoint was time to progression to symptomatic disease. Secondary endpoints were response rate, overall survival, and safety. After a median follow-up of 40 months, the median time to progression was significantly longer in the treatment group than in the observation group (median not reached vs. 21 months; hazard ratio for progression, 0.18; 95% confidence interval [CI], 0.09 to 0.32; $P < 0.001$). The 3-year survival rate was also higher in the treatment group (94% vs. 80%; hazard ratio for death, 0.31; 95% CI, 0.10 to 0.91; $P = 0.03$). A partial response or better was achieved in 79% of patients in the treatment group after the induction phase and in 90% during the maintenance phase. Toxic effects were mainly grade 2 or lower. Early treatment for patients with high-risk smoldering myeloma delays progression to active disease and increases overall survival. (NCT00480363).

Despite the promise of early treatment in the precursor MM disease setting, it has remained highly controversial given the high cost and risk of toxicity and harm to patients who may never progress to overt MM.¹⁴⁻¹⁶ For example, the treatments currently being investigated in the precursor disease setting carry considerable short- and long-term risks, including but not limited to arterial thromboembolic events, neutropenia and thrombocytopenia, and increased risk for secondary malignancies.¹⁷ These toxicities, in effect, mostly limit the use of existing therapies to the highest risk patient subsets. Therefore, the identification lower-risk, cost-effective strategies to prevent disease progression in patients with less aggressive forms of MGUS and SMM is of considerable importance.

2.3 Metformin

Metformin is a biguanide derivative that is FDA approved for the treatment of type 2 diabetes but is also considered safe for use in non-diabetic populations;¹⁸ serious adverse events are rare and are mostly limited to lactic acidosis. Metformin decreases hepatic glucose production, decreases intestinal absorption of glucose, and improves insulin sensitivity by increasing peripheral glucose uptake and utilization. Metformin, at therapeutic doses, does not cause hypoglycemia when used alone in man or in the non-diabetic animal, except when using a near lethal dose. Metformin has no effects on the pancreatic beta cells.

Metformin absorption is relatively slow, is delayed to some extent by food consumption, and may extend over a period of hours. The drug is excreted in urine at high renal clearance rate of about 642 mL/min, which varies based on dosage. The initial elimination of metformin is rapid with a plasma elimination half-life of approximately 6.2 hours. Metformin is not metabolized and is therefore excreted unchanged in the urine.

2.4 Trial Rationale

2.4.1.1 Clinical experience in cancer prevention

There is a growing body of literature indicating a benefit to the repurposing metformin in the cancer prevention setting, by demonstrating its efficacy in improving biological systems putatively associated with cancer prognosis among non-diabetics. For examples, in an observational cohort study using UK-based record-linkage databases, there was a significantly reduced risk of cancer associated with metformin use, with a hazard ratio for metformin reported to be 0.63 (95% CI, 0.53– 0.75). In this same study, total and cancer-specific mortality were also significantly lower among metformin users.¹⁹ In addition, a 2008 study among 32 non-diabetic breast cancer patients, which demonstrated that a 6-month intervention consisting of 1500mg of metformin significantly reduced fasting insulin and improve insulin sensitivity.²⁰ More recently, a univariate interim analysis among 492 non-diabetic breast cancer survivors enrolled in the NCIC Clinical Trials Group (NCIC CTG) MA.32 trial of metformin vs. placebo found metformin use for 6-months to be associated with improved glucoregulation (insulin, glucose, HOMA-IR), in addition to leptin and C-reactive protein.²¹

2.4.2 Rationale for investigation in precursor MM

Metformin is of particular interest as a disease interception tool in the precursor MM setting given that it is relatively inexpensive and is sustainable for long-term risk reduction,²²—all of which are characteristics that the current investigational therapies do not possess. The converging lines of evidence supporting the benefit of metformin in preventing MGUS/SMM progression are briefly outlined below:

In vivo and *in vitro* xenograft models have demonstrated metformin’s ability to inhibit MM cell proliferation by inducing apoptosis and cell cycle arrest through mechanisms of action that include the IGF-1R/PI3K/AKT/mTOR signaling pathway;²³ it also appears to work synergistically with other MM therapies, including dexamethasone,²³ bortezomib²⁴ and ritonavir²⁵ to limit MM cell proliferation. Metformin has also been shown to regulate other aspects of the bone marrow microenvironment in ways that may inhibit myelomagenesis, including but not limited to reducing bone marrow adipose tissue, which is a highly active endocrine organ that resides directly in the bone marrow niche and supports MM cell proliferation, as well as immune cells.^{26,27}

Data from observational studies further support the use of metformin in preventing disease progression in individuals with MGUS/SMM. For example, metformin use was associated with a statistically significant 53% reduced risk of MM in a cohort of 2,003 diabetics diagnosed with MGUS (95% CI: 0.25, 0.87),²⁸ and similar observations were reported in an independent cohort of MGUS patients from The Health Improvement Network.²⁹ Given the consistent laboratory science and epidemiologic evidence suggesting a beneficial role of metformin in regulating the activity of MM and other bone marrow niche cells, a number of ongoing clinical trials are testing its efficacy (in combination with other drugs) for the treatment of MM patients with relapsed and refractory disease (see ClinicalTrials.gov). However, we are not aware of any ongoing or planned clinical trials investigating the use of metformin in patients with MGUS or SMM.

2.4.3 M-Protein and Light-chain Concentrations as Clinically Relevant Disease Endpoints.

Monoclonal (M-)proteins and light chains produced in excess by an abnormal clonal proliferation of plasma (MM) cells that can be measured in the serum using Serum Protein Electrophoresis (SPEP) and the Serum Free Light Chain Assay. These quantitative tests usually correlate with overall tumor burden, and thus the SPEP is one of the most common clinical tests used to monitor patients with all stages of the disease continuum (MGUS, SMM and MM). Importantly, concentrations of these biomarkers have been repeatedly shown to reduce after treatment with a range of mild and aggressive MM therapies,³⁰⁻³² underscoring their utility as a sensitive and measurable marker of tumor response to treatment.³³

2.4.4 Mass Spectrometry

Quantitative immunopurification mass spectrometry (QIP-MS) combines Ig immunopurification with mass spectrometry resulting in a methodology that is more sensitive and specific than serum protein electrophoresis (SPEP) and immunofixation (IFX). The technique works by first isolating Ig’s using isotype specific beads. Purified Ig’s are then separated into light chains and heavy chains by the addition of a reducing agent. A mass spectrometer is then used to detect a monoclonal light chain from an M-protein observed as a peak above the normal polyclonal

background. Mills et al. demonstrated that QIP-MS could detect an M-protein in patient serum when SPEP and IFX were negative.³⁴ They also showed in serial dilution studies that a monoclonal light chain peak could be detected by QIP-MS at a level < 0.05 g/L; a level that was negative when analyzed by SPEP and IFX. The specificity of QIP-MS is provided by the superior resolving capability and mass measurement accuracy of the mass spectrometer.

Barnidge and colleagues demonstrated that molecular mass could be used to monitor a specific monoclonal kappa light chain in a patient GK MM over a 7-year period.³⁵ The monoclonal light chain could easily be detected in samples that were negative by SPEP and IFX. Multiple clones can be easily identified in serum using QIP-MS technology since the mass spectrometer provides superior resolution compared to gel electrophoresis. M-protein quantification is performed by comparing monoclonal light chain peak intensities with an internal reference.

2.5 Correlative Studies Background

2.5.1 Immune cell characterization in the peripheral blood and bone marrow

Tumors are complex ecosystems characterized by interactions between heterogeneous cell types, including malignant cells and immune cells³⁶. An important step in the progression of tumors is their ability to evade and suppress the host immune system in a way that fosters immune escape and tumor growth.^{37,38} Therefore, therapies that modify immune microenvironment may be effective anti-myeloma therapies.³⁹ For example, metformin can interfere with immunopathological mechanisms implicated in MGUS/SMM disease progression,⁴⁰ including but not limited to the T helper 17/regulatory T cell balance, cytokine synthesis, and natural killer cell response,^{39,41,42} suggesting that the putative benefits of metformin on the prevention of disease progression in MGUS/SMM may be mediated, in part, through the effects on the immune microenvironment.

2.5.2 Value of Metabolomics

Metabolomics, e.g., the high-throughput identification and quantification of small molecule metabolites produced by metabolism, can yield novel insights into pathogenesis and risk of cancer and chronic disease.^{43,44} Metabolomics is the study of metabolic changes in biological systems and provides the small molecule fingerprints that reflect the complex relationships between diet, lifestyle (obesity), genes, and disease processes.⁴⁴ We believe that metabolomics offers a unique lens to study progression in the precursor MM, given that of all molecular entities (e.g., genes, transcripts, proteins, metabolites), metabolites have the closest relationship to expressed phenotype, as they are the final endpoints of biochemical processing.⁴⁵ Despite the growing interest and application of metabolomics to cancer and chronic disease research, metabolomics-based studies of MM, MGUS, or SMM are sparse.⁴⁶⁻⁵¹ One small study by Ludwig et al identified 25 bone marrow metabolites that differed between 10 MGUS and 10 MM patients,⁴⁶ but this work has not yet been expanded in larger samples with clinical and lifestyle data. A larger metabolomics investigation of precursor MM patients could contribute important knowledge regarding the landscape of the metabolic changes underlying the disease, and ultimately lend important insights into interception strategies and druggable targets. Particularly important categories of metabolites

in cancer and metabolic disease are metabolites of glycolysis and the TCA cycle. These are of interest to the current study because of their critical role in tumor growth^{52,53} and because they have been shown to be obesity related.⁵⁴ Importantly, these metabolite categories have consistently shown to be sensitive to metformin⁵⁵⁻⁵⁷—likely because of their relationship to the mammalian target of rapamycin (mTOR),^{58,59} which is the cellular signaling cascade that serves as a master regulator of metabolism, cell growth, and proliferation.⁶⁰

2.5.3 Quality of life in the Precursor Disease Setting

As an exploratory objective, given the high rates of anxiety and distress document in individuals with MGUS and SMM^{61,62} and lack of evidence-based risk reduction strategies available for preventing disease progression to MM, we will explore the psychosocial benefits of offering a low-risk pharmacologic intervention to this patient population.

3. PARTICIPANT SELECTION

3.1 Eligibility Criteria

3.1.1 Diagnosed with high-risk MGUS or low-risk SMM⁶³ defined below:

Higher-Risk MGUS: bone marrow plasma cell concentration <10%# AND either serum M-protein level ≥ 1.5 g/dL to <3 g/dL, abnormal free light-chain (FLC) ratio (<0.26 or >1.65), or IgA MGUS.

Note: individuals with an abnormal FLC ratio that are classified as light-chain only are eligible. Light-chain only patients are defined as complete loss of immunoglobulin heavy-chain, accompanied by abnormal FLC ratio with an increased level of the appropriate involved light-chain (increased kappa FLC in patient with ratio >1.65, and increased lambda FLC in patients with ratio <0.26).

Low-Risk Smoldering Myeloma: bone marrow plasma cells $\geq 10\%$ # with the absence of additional high-risk features, which are further defined in the exclusion criteria (3.2.1)⁶⁴

#A new bone marrow biopsy is preferred for plasma cell determination at screening; however, determination of eligibility can be made from most recent bone marrow biopsy performed as long as it was within 2 years of enrollment.

3.1.2 Absence of evidence of CRAB criteria* or new criteria of active MM or active WM which including the following (note if one or more criteria has not been evaluated (e.g., no MRI), the criteria for active MM or WM for that feature is considered unmet):

- Increased calcium levels (corrected serum calcium >0.25 mmol/dL above the upper limit of normal or >0.275 mmol/dL) related to MM
- Renal insufficiency (attributable to MM)

- Anemia (Hb 2g/dL below the lower limit of normal or <10g/dL) related to MM
- Bone lesions (lytic lesions or generalized osteoporosis with compression fractures)
- Bone marrow plasma cells $\geq 60\%$
- Serum involved/uninvolved FLC ratio ≥ 100 , provided the absolute level of the involved free light chain is at least 100 mg/L and repeated twice (light chain smoldering myeloma as described in section 2.4 is not an exclusion criteria).
- MRI with two or more focal lesion that is at least 5 mm or greater in size
- Hyperviscosity symptoms per WM guidelines for symptomatic WM

**Participants with CRAB criteria that are attributable to conditions other than the disease under study may be eligible*

3.1.3 At least 18 years of age.

3.1.4 Eastern Cooperative Oncology Group (ECOG) performance status of 0, 1, or 2.

3.1.5 The following laboratory values obtained prior to the first dose of study drug/placebo:

- AST and ALT $< 1.5 \times$ institutional ULN
- Serum bilirubin $<$ institutional ULN (in patients with Gilbert's Disease, direct bilirubin $<$ institutional ULN)
- Calculated creatinine clearance $\geq 45 \text{ mL/min}$
 - Estimation of renal function will be assessed using the CrCl calculated based on the Cockcroft-Gault formula:
 - $\text{CrCl} (\text{mL/min}) = (140-\text{age}) (\text{weight} [\text{kg}]/72 (\text{serum creatinine} [\text{mg/dL}])$; for females the formula is multiplied by 0.85
- Random glucose $< 160 \text{ mg/dL}$ or fasting glucose $< 126 \text{ mg/dL}$ (other values require workup to rule out undiagnosed diabetes that may require treatment)

3.1.6 Ability to understand and the willingness to sign a written informed consent document

3.1.7. For participants who wish to enroll in the open label extended treatment (crossover arm), participants can be unblinded and learn of their drug group AFTER completing primary endpoint collection. Patient must be randomized to metformin in order to continue taking metformin for 6 additional months.

3.3 Inclusion of Women and Minorities

Both men and women of all races and ethnic groups are eligible for this trial.

4. REGISTRATION AND RANDOMIZATION PROCEDURES

4.1 Recruitment

Participants will be primarily recruited from the Center for the Prevention of Progression (CPOP) Clinic at Dana-Farber, but we may expand recruitment to other Mass General Brigham sites. We will utilize multiple active recruitment techniques to maximize participation and generalizability. We will use the following strategies to identify potential participants:

- We will review clinic schedules and patient lists at DFCI and other Partners Healthcare institutions. HIPAA waivers will be obtained prior to review of these patient lists.

Once a potential participant is identified, they will be contacted by phone/email by a study coordinator to solicit interest, or during a clinic visit or through other approved methods of communication.

Interested subjects identified through these recruitment strategies will be pre-screened by study staff either in person or by phone initially and if potentially eligible, he or she will meet with a member of the study staff to review the protocol and sign informed consent.

Consenting will occur in person or remotely via 45 CFR part 46, local CON-100 and 21 CFR part 11 compliant Adobe eSign. Adobe eSign consent may be utilized for patients who have recently been seen by study clinicians, but who live far away/ out of state and are unwilling to return to the main campus to consent to study. Participants that are consented electronically will utilize the same version as the paper version of the consent form. Patients will be provided with a copy of the consent form. They will have the opportunity to discuss and ask questions about the study with their clinician prior to signing consent form and discuss any potential questions with study staff. Once review of the consent has concluded, the study staff will email another consent form via Adobe eSign Consent through an official Dana-Farber email to the participant's authenticated and confirmed email address that is on file in their medial record.

4.2 Registration process

All eligible participants who consent and wish to enroll in the intervention will be registered in the Clinical Trials Management System (CTMS) OnCore. Registrations must occur prior to the initiation of any protocol-specific therapy or intervention. Any participant not registered to the protocol before protocol-specific therapy or intervention begins will be considered ineligible and registration will be denied. Any participant who wishes to become unblinded after primary endpoint completion and is interested and eligible to enroll in the open-label crossover arm of the study must be registered to the crossover arm in OnCore.

An investigator will confirm eligibility criteria and a member of the study team will complete the protocol-specific eligibility checklist.

The eligibility checklist(s) and all pages of the consent form(s) will be faxed or emailed to ODQ at [contact]. The ODQ will (a) review the eligibility checklist, (b) register the participant on the protocol, and (c) randomize the participant.

Randomization can only occur during ODQ business hours (8:30am - 5pm Eastern Time, Monday through Friday excluding holidays).

The ODQ Protocol Systems Coordinator is responsible for randomizing subjects to treatment arms for investigator-sponsored research

The statistician in the Department of Biostatistics and Computational Biology provides ODQ with any necessary randomization sheets and instructions specific to the protocol.

For blinded protocols: The ODQ Protocol Systems Coordinator conveys the randomization assignment to the appropriate departments as directed by the randomization instructions.

An email confirmation of the registration and/or randomization will be sent to the study coordinator(s) from the registering site, treating investigator and registering person immediately following the registration and/or randomization.

Following registration, participants may begin protocol-specific therapy and/or intervention. Issues that would cause treatment delays should be discussed with the Principal Investigator (PI) of the registering site. If the subject does not receive protocol therapy following registration, the subject must be taken off study in the CTMS (OnCore) with an appropriate date and reason entered.

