5. TREATMENT PLAN

We will conduct a randomized placebo-controlled trial in patients with higher-risk monoclonal gammopathy of undetermined significance (MGUS) and low-risk smoldering multiple myeloma (SMM). After informed consent is signed, total of 60 eligible and evaluable participants will be randomized 1:1 either to metformin or placebo. Stratification factors will be disease stage (MGUS vs. SMM) and heavy vs. light-chain status. The treatment period will be 6 months and primary outcome assessments as outlined below will occur at baseline and after 6 months of treatment or for those that discontinue medication, as close to the 6-month timepoint as possible. To explore participants' willingness to continue to take metformin after the 6-month treatment period and observe longer-term response, participants will be given the option to learn their treatment assignment after completing the primary study endpoints. Any participant randomized to the metformin group will be invited to continue to take metformin for an additional 6 months.

Treatment will be administered on an outpatient basis. Reported adverse events and potential risks are described in Section 7. Appropriate dose modifications are described in Section 6.

Participants will dose escalate in a stepwise fashion beginning with 500mg and increasing by 500mg until they reach 1500mg. The duration of this study and corresponding treatment period is 6 months.

No investigational or commercial agents or therapies other than those described below may be administered with the intent to treat the participant's premalignancy.

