5.9 Removing a Participant from Study (Off Study/Off Follow Up)

Participants will be removed from study when any of the following criteria apply:

- Lost to follow-up
- Withdrawal of consent for data submission
- Death
- Progression to overt MM

The reason for taking a participant off study, and the date the participant was removed, must be documented in the case report form (CRF). In addition, the study team will ensure the participant's status is updated in OnCore in accordance with [REGIST-OP-1](#).

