9. STUDY MEASURES

9.1 Screening/Baseline Assessments

After the prospective participant signs the informed consent form, eligibility will be assessed including review of medical history and clinical blood tests. To minimize additional visits to DFCI during the COVID-19 pandemic, all in-person screening assessments as well as any baseline measures that require in-person collection will occur at the time of a scheduled clinical appointment at DFCI.

All clinical blood tests to confirm eligibility will be reviewed by a clinician; any values outside the normal range will be discussed with the patient's primary oncologist. Participants meeting eligibility criteria will be randomized to metformin or its corresponding placebo and ideally will be mailed the medication/placebo no later than 5 business days after randomization occurs unless a later date is requested by the participant. The participant will be instructed to begin taking the study medication upon receipt.

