12.2 Statistical Analysis

The primary hypothesis being tested in this trial is that patients randomized to metformin will experience a significant reduction in M-protein levels compared to patients randomized to the placebo. This parameter has been selected as the primary endpoint because of its known clinical utility in predicting progression to overt MM in MGUS and SMM patients.⁶⁷⁻⁶⁹ Changes in this endpoint will be evaluated from baseline to follow-up in the two groups using a repeated measures mixed-effects model that accounts for the correlation between baseline and follow-up measures and is generally robust to missing data. The baseline value of the dependent variable (M-protein level) and disease subtype will be included as covariates in the regression models. Group-by-time interaction terms will be included as fixed-effects in the regression model. Model fit will be assessed using standard methods. Primary analysis of this endpoint will utilize stratified testing and intention-to-treat methods, using data from all participants randomized to an intervention group.⁷² Secondary/exploratory analyses will evaluate the influence of metformin on M-protein level in a per-protocol analysis.

A study project manager who is not involved in the statistical analysis will request information on treatment allocation from the DFCI Research Pharmacy. The Research Pharmacy is permitted to give the project manager information after the trial is closed to accrual and data collection on primary endpoints have been completed. However, all individuals performing the statistical analysis will remain blind to treatment group (metformin vs. placebo) for the primary outcome analysis.

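### Section 4.2 takes randomised participants who never receive study drug off study, probably ending their 6-month M-protein follow-up, which is inconsistent with intention to treat on all randomised

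*Combined protocol and SAP*

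**What the plan says.** All references are to the combined protocol and SAP.

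- **Section 4.2** gives the order of events at the Office of Data Quality (ODQ). After checking eligibility it will "b) register the participant on the protocol, and (c) randomize the participant". The section closes with the rule at issue: "If the subject does not receive protocol therapy following registration, the subject must be taken off study in the CTMS (OnCore". A date and reason are to be recorded. The sentence just before it sends treatment delays to the site's principal investigator for discussion.
- **Section 9.1** puts drug supply after randomisation. Participants "ideally will be mailed the medication/placebo no later than 5 business days after randomization occurs unless a later date is requested by the participant", and they begin taking it when it arrives.
- **Sections 5.7 and 5.9** separate leaving treatment from leaving the study. Section 5.9, whose heading treats off study and off follow-up as one status, says "Participants will be removed from study when any of the following criteria apply". It lists four reasons: loss to follow-up, withdrawal of consent to data submission, death, and progression to overt myeloma.
- **Sections 5, 9.2 and 10** keep the 6-month assessment, as near to 6 months as feasible, for people who discontinue or do not complete treatment. Section 5.8 adds record follow-up for up to 5 years from randomisation.
- **Section 12.2** commits the primary analysis to "intention-to-treat methods, using data from all participants randomized to an intervention group". Section 12.8, which covers exclusions, repeats the intention-to-treat commitment and names no exclusion.

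**The concern.** Between randomisation and the first capsule there is a mailing interval in which a participant may change their mind or fall ill. That person already has an assigned arm and a baseline M-protein value. Section 4.2 then makes removal from the study mandatory, although nothing about not taking a capsule prevents a blood draw six months later.

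At stake is whether the intention-to-treat commitment can be carried out. An analysis of everyone randomised needs outcomes from everyone randomised, as far as they can be obtained. A rule that switches off outcome collection because treatment did not begin creates missing primary outcomes that were avoidable. The sample size in section 12.1 carries no allowance for dropout to absorb them.

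**Working it through.** **1. Does the rule reach randomised people?** Yes. Section 4.2 triggers on not receiving therapy after registration. Registration and randomisation are consecutive ODQ steps, and section 9.1 mails drug only after randomisation. No section exempts randomised participants.

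**2. What follows from being off study?** Section 4.2 does not say that the 6-month visit is cancelled. Section 5.9's heading equates off study with off follow-up, and no section schedules an assessment for someone already off study. Loss of the visit is therefore a probable reading, not a stated one.

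**3. The provisions side by side.**

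| After randomisation | Governing text | 6-month M-protein |
|---|---|---|
| Completes treatment | 9.2, 10 | Scheduled |
| Takes one dose, then stops | 5, 9.2, 10 | Scheduled near 6 months |
| Never receives drug | 4.2 read with 5.9 | No provision; probably lost |

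The second and third rows differ by one dose, and the documents give no reason for treating them differently. Never starting is also absent from section 5.9's own list.

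**4. Can the model recover the loss?** Hardly. Section 12.2 uses a mixed model with a single post-baseline timepoint and baseline as a covariate. A participant with only a baseline value can stay in the dataset but adds essentially nothing to the 6-month comparison between arms.

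**5. Size.** Inputs from section 12.1: SD 0.99 g/dL, type I error 0.05, 60 participants (30 per arm), differences of 0.73 and 0.84 g/dL, stated power 80% and 90%. Sidedness is not stated.

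Formula: noncentrality = d / (SD × √(1/n₁ + 1/n₂)). Power comes from the noncentral t distribution on n₁ + n₂ − 2 degrees of freedom, two-sided 0.05.

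Reproducing the plan: 0.99 × √(2/30) = 0.2556.
- 0.73 / 0.2556 = 2.86, power 80.2%.
- 0.84 / 0.2556 = 3.29, power 89.8%.

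The normal approximation gives 81.5% and 90.8%. Both match the stated figures. One-sided 0.05 gives 88.7% and 95.0% and does not.

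Now remove 6-month values. The counts are assumptions, because the documents give no never-start rate.

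| Lost (per arm) | Share of 60 | Power, 0.73 g/dL | Power, 0.84 g/dL |
|---|---|---|---|
| 0 | 0% | 80.2% | 89.8% |
| 2 (1+1) | 3.3% | 78.8% | 88.8% |
| 4 (2+2) | 6.7% | 77.3% | 87.7% |
| 6 (3+3) | 10% | 75.8% | 86.4% |

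**6. What keeping them does.** Suppose 0.73 g/dL is the effect in people who take metformin, and never-starters in that arm have none. Analysing all 60 with one never-starter per arm gives an expected difference of 0.73 × 29/30 = 0.706 and power of 77.5%. With two per arm it is 0.73 × 28/30 = 0.681 and 74.6%. These are slightly below the 78.8% and 77.3% obtained by losing the values. The reason to keep these participants is therefore that the analysis then answers the question section 12.2 sets, not that it gains power.

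**The case against.** The strongest case on the other side is that section 4.2 is a status instruction for the trial management system, placed in a registration section, and not an analysis rule. What off-study status permits depends on institutional procedures that the protocol cites but does not reproduce. Sections 9.2 and 10 provide for people who could not complete six months of treatment, which can be read to include those who never began. On that view the intent is to assess everyone, and one template-like sentence is out of line. Some never-starters would also withdraw consent and be lost under section 5.9 in any case.

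Much of this stands. It is why the loss of the visit is put as probable, and why the effect is called small. It does not remove the inconsistency. The rule is worded as mandatory, and the generous reading of section 9.2 itself conflicts with section 4.2, so the text needs reconciling either way.

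A reader might infer three stronger things that the documents do not support:

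- **That the primary analysis becomes one of randomised and dosed participants.** Section 12.2 still defines the set as "using data from all participants randomized to an intervention group", and section 4.2 defines no analysis set. A never-starter is a case with a missing outcome, the same data pattern as someone who takes one dose and is then lost.
- **That never-starters would be replaced.** Section 5 says "total of 60 eligible and evaluable participants will be randomized 1:1 either to metformin or placebo", but no section provides for replacement, and sections 1.1 and 12.3 give a plain target of 60.
- **That a late start triggers removal.** Section 4.2 refers delays to the principal investigator, and section 9.1 allows later mailing on request.

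**Conclusion.** The inconsistency is real and modest. Section 4.2 requires removal from the study for an event that concerns treatment only, it applies after randomisation, and read with section 5.9 it probably ends collection of the primary outcome. That does not fit sections 12.2 and 12.8, or the 6-month assessment preserved in sections 5, 9.2 and 10.

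The number affected is unknown and probably small. On an assumed 2 to 4 of 60, the cost is about 1.4 to 2.9 percentage points of power for 0.73 g/dL (80.2 − 78.8 and 80.2 − 77.3). Little bias between arms is expected: assignment is blinded and these participants have taken nothing, so the decision not to start should not depend on arm. This rests on the blind holding and on section 5.9's heading meaning what it says.

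One point of wording stays open. Section 4.2 speaks of not receiving therapy, and it is unclear whether someone who was mailed drug but never took it is covered.

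**What to change.** Reconcile section 4.2 with sections 5.7, 5.9, 9.2 and 12.2. State that a randomised participant who never receives or never starts study drug:

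- is recorded as off treatment, with date and reason;
- stays on study unless consent is withdrawn;
- has SPEP and serum free light chains at the 6-month timepoint, from a routine clinical draw where possible, and the planned record follow-up;
- is analysed in the assigned arm.

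Using both terms, receives and starts, settles the ambiguity over mailed but untaken drug. No dose or treatment rule changes.

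The cost is a wording amendment, a few additional blood draws at most, and a slight dilution of the estimated effect, which is inherent in the intention-to-treat comparison the plan has already chosen.
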